6.8.2.3 Supportive/sensitivity analyses

Not applicable.

6.8.2.4 Subgroup analyses

Descriptive summaries will be provided for each secondary PD endpoint, i.e., PD profile over time, and PRU_{60m} status, using the same sub-groups as defined in Section 6.8.1.4.

6.8.3 Handling of missing data

No imputations are planned.

Subjects for whom determination of the PD response is not possible will not be included in the computation of response rate for the main analysis.

The same approach will be considered for the exploratory endpoint PD response within the 1st hour.

6.9 Analysis of pharmacokinetic variables

The PK variables will be summarized and listed as provided using the PK set and will use the study treatment received.

The plasma PK parameters of ACT-246475 will be derived by non-compartmental analysis of the plasma concentration-time profiles. PK endpoints are: Maximum plasma concentration (C_{max}), and time to reach C_{max} (t_{max}).

Log-transformed value of C_{max} will be used in the analysis, while t_{max} will be used as is.

The PK parameters t_{max} , and $\log(C_{max})$ will be summarized by dose group using descriptive statistics, i.e., arithmetic mean, SD, geometric mean, minimum, median, maximum, standard error, and two-sided 95% CI of the means and coefficient of variation in %. Graphical representation of PK results over time will be provided using box-whisker plots.

Note that for t_{max} , the geometric mean and its 95% CI will not be calculated.

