##### *7.2.3.1.2 Bioanalysis*

The analysis of ACT-246475 in plasma will be performed using a validated liquid chromatography coupled to tandem mass spectrometry assay.

The foreseen lower limit of quantification is 1 ng/mL. Concentrations will be calculated by interpolation from a calibration curve.

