## **10 STATISTICAL METHODS**

All statistical analyses will be conducted by sponsor or by designated CROs supervised by sponsor.

A statistical analysis plan (SAP) will provide full details of the analyses, data displays, and algorithms to be used for data derivations.

Any deviation(s) from the statistical plan described hereafter will be described and justified in the SAP or in the clinical study report (CSR), as appropriate.

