### 10.2.3 Pharmacokinetic and pharmacodynamic variables

#### 10.2.3.1 Pharmacokinetic variables

PK parameters will be derived using non-compartmental methods:

- $C_{max}$  and  $t_{max}$  will be listed by dose group and subject and will be summarized by dose group.
- $C_{max}$  and  $t_{max}^*$  will be summarized with arithmetic mean, geometric mean, minimum, median, maximum, standard deviation (SD), standard error (SE), coefficient of variation (CV; %), and 95% confidence interval (CI) of the arithmetic and geometric means.

(\* For  $t_{\max}$  the geometric mean and its 95% CI will not be calculated).

- Log-transformed  $C_{\max}$  values will be summarized by mean and SD of the logarithms.

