11.3 Clarifications concerning endpoint definitions and related variables or statistical methods

Analysis set

The PPS definition has been modified to use the analysis set used for analysis of primary endpoint as a reference. Instead of using the FAS as the reference set to define the PPS, the mFAS is used and is more relevant as this analysis set is the one used for performing the analyses on the primary PD endpoint.

The protocol indicated that analysis of *demographics characteristics* would be performed on the RND only if there was a difference between the RND and the set used for the main analysis (FAS). The SAP now requires that this analysis is performed on the RND as well, regardless of the difference to the FAS, unless the RND includes exactly the same subjects, in which case the analysis on the RND is not needed.

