12 LIST OF TABLES, LISTINGS AND FIGURES

A complete list of tables, listings and figures is provided in the *SAP Appendix - List of statistical outputs* document.

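### SAP 6.9 as written puts the geometric mean and CV% on log(Cmax), not on Cmax as in protocol 10.2.3.1, and records no change; the protocol rule should be restored.

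*SAP*

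**What the plan says.** **Protocol, section 10.2.3.1.** Cmax and tmax, on their original scale, "will be summarized with arithmetic mean, geometric mean, minimum, median, maximum, standard deviation (SD), standard error (SE), coefficient of variation (CV" in percent), with 95% confidence intervals of the arithmetic and geometric means. A footnote drops the geometric mean and its interval for tmax. A separate bullet covers log-transformed Cmax, whose "values will be summarized by mean and SD of the logarithms", and asks for nothing more.

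**SAP, section 6.9.** The section opens with a general line: "The PK variables will be summarized and listed as provided using the PK set and will use the study treatment received". It names Cmax and tmax as the PK endpoints, then says that the analysis uses Cmax after log transformation and tmax untransformed. The sentence that sets the statistics has two subjects, tmax and log(Cmax), and these "will be summarized by dose group using descriptive statistics, i.e., arithmetic mean, SD, geometric mean, minimum, median, maximum, standard error", followed by two-sided 95% confidence intervals and CV%. A closing note removes the geometric mean for tmax only. No list of statistics is given for untransformed Cmax.

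**Change control.** Protocol section 10 says: "Any deviation(s) from the statistical plan described hereafter will be described and justified in the SAP", or alternatively in the study report. SAP section 11 is the place for such entries, and its section 11.3 is headed "Clarifications concerning endpoint definitions and related variables or statistical methods". Nothing in section 11 concerns PK.

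**The concern.** Moving the list from Cmax to log(Cmax) changes what two of the statistics mean. A geometric mean is a sensible summary of Cmax because it is the exponential of the mean log. Taken on values that are already logarithms, it has no useful interpretation. It also fails if any logarithm is negative, and is zero if one is zero. A CV% is meaningful on a ratio scale. Logarithms of a concentration have an arbitrary zero, set by the unit, so their SD divided by their mean has no fixed meaning.

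Assessing PK in acute MI is a stated objective (protocol 2.2). Protocol 1.3 gives the reason: peripheral vasoconstriction may affect uptake from the injection site. Between-subject variability in Cmax is a natural descriptor of uneven uptake, and the results are meant to support the Phase 3 dose choice (protocol 4.2). A CV% column that understates that variability several-fold would mislead a reader on this point.

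**Working it through.** The plan states no figure on this point, so there is none to reproduce. The check is a comparison of texts followed by an illustration of size.

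**1. Side by side**

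| Variable | Protocol 10.2.3.1 | SAP 6.9 as written |
|---|---|---|
| Cmax, original scale | full list, including geometric mean and CV% | no list given |
| log(Cmax) | mean and SD only | full list, including geometric mean and CV% |
| tmax | full list, no geometric mean | full list, no geometric mean |

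**2. Is the change recorded?** SAP 11.1.1 concerns the analysis set for the PD sensitivity analysis. SAP 11.1.2 concerns the set for exposure. SAP 11.3 concerns the per-protocol definition and the set for demographics. SAP 11.2 and 11.4 are marked not applicable. None mentions PK.

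**3. Size of the CV% error.** Inputs: no Cmax values are visible, so a lognormal Cmax is assumed with true CV 30%, 50% or 70% and geometric mean (GM) 50 to 500 ng/mL.

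- SD of ln(Cmax) = sqrt(ln(1 + CV²)), which gives 0.2936, 0.4724 and 0.6315 for CV 30%, 50% and 70%.
- CV% of the logs = SD / ln(GM), with ln(50) = 3.912 and ln(500) = 6.215.

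| True CV of Cmax | CV% of logs, GM 50 | CV% of logs, GM 500 |
|---|---|---|
| 30% | 0.2936/3.912 = 7.5% | 0.2936/6.215 = 4.7% |
| 50% | 0.4724/3.912 = 12.1% | 0.4724/6.215 = 7.6% |
| 70% | 0.6315/3.912 = 16.1% | 0.6315/6.215 = 10.2% |

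The size depends on the assumed GM. For the logs to show 50% when the true CV is 50%, ln(GM) would have to be 0.4724/0.50 = 0.945, a GM of about 2.6 ng/mL. That is close to the assay limit ("The foreseen lower limit of quantification is 1 ng/mL"). At the in vitro IC50 of 8.7 ng/mL in protocol 1.2.1, the reading would be 0.4724/2.163 = 21.8%.

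**4. Dependence on the unit.** Take GM 100 ng/mL and CV 50%. In ng/mL, 0.4724/4.605 = 10.3%. In µg/mL the same data give ln(0.1) = −2.303 and 0.4724/(−2.303) = −20.5%. With 21 evenly spaced lognormal quantiles, every log is then negative, so their geometric mean is undefined. On the original scale, the CV does not change with the unit and the geometric mean merely rescales.

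**5. Sampling variation with 21 subjects in an arm.** In 200,000 simulated lognormal samples with true CV 50%, the CV% of the logs fell in 95% of samples between 8.3% and 15.9% at GM 50, and between 5.3% and 9.9% at GM 500.

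**6. The geometric mean.** In the same simulation the geometric mean of the logs averaged 3.884 (GM 50) and 6.197 (GM 500), against arithmetic means of 3.912 and 6.215. A reader who exponentiated it would be only 2.7% and 1.7% too low. The CV% is therefore the misleading column.

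**7. Recoverability.** The same SAP sentence reports the mean and SD of the logs. Exp(mean) returns the geometric mean of Cmax, and sqrt(exp(SD²) − 1) returns a lognormal CV. In the simulation the latter had a median of 49% (95% range 34% to 68%) for a true value of 50%.

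**The case against.** The strongest reply is that the SAP's intent agrees with the protocol and only the wording slipped. SAP 6.9 names untransformed Cmax as an endpoint, and its general opening line may cover Cmax. Its closing note on tmax repeats the protocol's footnote, which belongs to a table where the geometric mean is that of Cmax. A geometric mean is ordinarily computed through logs, so mentioning the log transformation may only describe the route. The wording on intervals and CV% also resembles protocol 10.3.4, where it applies to untransformed plasma concentrations, which suggests copying.

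Much of this stands as an account of how the sentence arose. It does not settle what is to be produced. SAP 6.9 mentions no back-transformation, and reading the geometric mean that way leaves the CV% on the logs. The opening line specifies no statistics for Cmax and removes none from log(Cmax). Summaries of concentrations by time point under protocol 10.3.4, if produced, might make a very low CV% for Cmax look odd, but they do not correct the rule.

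Other points stand as limits:

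- The numbers rest on assumed Cmax values.
- SAP section 12 says "A complete list of tables, listings and figures is provided in the" separate outputs document. Neither that document nor the table shells are available, so the final table may be right.
- Protocol section 10 allows a deviation to be explained in the study report, so silence in the SAP is not in itself a breach.
- PK is an exploratory, descriptive objective, and the correct values can be recovered.

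**Conclusion.** The concern holds, as a statement about the wording. SAP 6.9, followed literally, takes the geometric mean and CV% on log(Cmax), contrary to protocol 10.2.3.1, and SAP section 11 does not record the change. Within the assumed range (true CV 30% to 70%, geometric mean 50 to 500 ng/mL, natural logs of ng/mL), the CV% column would read 4.7% to 16.1%; for a true CV of 50% it would show roughly one quarter to one seventh of the real figure (12.1/50 = 0.24, 7.6/50 = 0.15). The direction is secure unless Cmax lies close to the assay limit; the exact size is illustrative.

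The consequence is modest: a misleading column in a descriptive table, with no effect on the primary PD test, its alpha, the power or the sample size. Certainty is high about the text and does not extend to the table that will finally be produced. It should be corrected, because the stated rule gives a wrong result if followed and the protocol already contains the right one.

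**What to change.** In SAP 6.9, replace the sentence that summarizes tmax and log(Cmax) with one that follows protocol 10.2.3.1, for example:

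> Cmax and tmax are described on the original scale by arithmetic mean, SD, SE, CV%, median, minimum, maximum and the 95% CI of the arithmetic mean. For Cmax only, the geometric mean and its 95% CI are added. For log(Cmax), only the mean and SD are given.

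Then check that the PK parameter table shell matches. If the change of scale was intended, record and justify it in SAP section 11 instead, or in the study report if the database is already locked.

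The cost is one sentence and one shell check, with no new data. The only downside is a slightly longer table, since Cmax and log(Cmax) both appear.

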7 SAFETY VARIABLES AND ANALYSES

7.1 Overview of safety analyses including subgroup analyses

For categorical variables, the incidence of subjects by category will be summarized by using frequency counts, and percentages.

Continuous variables will be summarized using: arithmetic mean, SD, minimum, 1st quartile, median, 3rd quartile, and maximum.

No sub-group analyses are planned for safety data.

7.2 Adverse events

The handling of missing or incomplete date/time of adverse events (AEs) and assessments is described in [Appendix D](#).

7.2.1 Variables

7.2.1.1 All adverse events

An AE is defined as any event that is recorded on the AE CRF form regardless of the onset date.

7.2.1.2 Treatment-emergent adverse events

Treatment-emergent AEs (TEAEs) are those AEs with onset date/time \geq date/time of study drug administration and \leq 48 h after date/time of study treatment administration.

An AE for which **time** of onset is missing will be counted as treatment-emergent if onset **date** is \geq date of study drug administration and is \leq date of study treatment administration +2 days. An AE with onset time missing, and end date and time are identical to study treatment start date and time, is not a treatment emergent AE.

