## 3 OVERALL STUDY DESIGN AND PLAN

### 3.1 Study design

This is a prospective, multi-center, open-label, randomized, parallel-group, Phase 2, exploratory study of a single s.c. administration of ACT-246475, at two different dose levels, in subjects with AMI (STEMI or NSTEMI) scheduled for invasive strategy.

Approximately 42 adult subjects with confirmed diagnosis of AMI (STEMI or NSTEMI) and time from onset of symptoms of more than 30 min and less than 6 hours will be randomized to receive ACT-246475 either at the dose of 8 mg or 16 mg, in a 1:1 ratio injected s.c. into the thigh in addition to conventional standard-of-care treatment. Injection of ACT-246475 will be performed as soon as possible after randomization.

Subjects randomized who have not received ACT-246475 or who do not perform the 30-minute time point VerifyNow® assessment will be replaced.

The study will be conducted at approximately 3–8 sites in 2–3 countries (planned).

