## **9.3 Reporting procedures**

### **9.3.1 Reporting of adverse events**

All AEs with an onset date after a subject has provided informed consent and up to the EOS must be recorded on specific AE forms of the eCRF.

Information to be collected in an AE form in the eCRF includes date and time of onset, action taken with the study treatment, outcome of AE, date of resolution (if applicable)

and Principal Investigator's (PI) assessment of intensity, and relationship to study treatment, study design or protocol mandated procedures.

If intensity of an AE changes during the study, only the worse intensity will be reported in the eCRF.

Follow-up information on an ongoing AE obtained after the subject's EOS will not be collected in the eCRF.

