#### **10.2.4 Safety variables**

##### **10.2.4.1 Adverse events**

An AE is defined as any event that is recorded on the AE eCRF module regardless of the onset date.

TEAEs are those AEs with onset date/time  $\geq$  date/time of study treatment administration and  $\leq$  48 h after date/time of study treatment administration.

The handling of missing or incomplete dates/time of AEs and assessments will be described in the SAP.

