Appendix D Handling of missing or incomplete date and/or time

This section describes some general principles to be followed in the case of missing or incomplete date/time.

Note that unless noted otherwise, the non-imputed date/time will be reported in listings.

An incomplete (missing day or month) or missing AE/concomitant therapy date will be imputed as described in Table 5. The ‘lower limit’ and ‘upper limit’ refer to the earliest and latest possible dates, respectively.

As an example: If the start date is MAR2017 (missing day), the lower limit is 01MAR2017 and the upper limit is 31MAR2017; If the start date is 2017 (missing day and month), the lower limit is 01JAN2017 and the upper limit is 31DEC2017.

Table 5 Handling of missing/incomplete date and time

Type of date	Date is incomplete	Date is missing
AE/CM end date	The upper limit.	No replacement, the AE/medication is considered as ongoing in the analysis.
AE/CM onset date	
Unless, the event is flagged as Started prior to first study treatment administration on the CRF*, the below rule applies.
 
If the (imputed) resolution date is on or after the start of the study treatment and if the start of the study treatment falls within the upper and lower limits (inclusive), the study treatment start date is used.
 
If the resolution date is missing and the study treatment start date falls within the upper and lower limits (inclusive) the study treatment start date is used.
 
In all the other cases the lower limit is used.
 
If the event is flagged PRIOR TO FIRST DOSE*; the study treatment start date –1 day is used.
	Whichever is the earlier of the date of resolution and the <study treatment> start date.

AE, adverse event; CM, concomitant medication; CRF, case report form.

Medical history dates will not be imputed. If separate reports need to be done for previous or concomitant medication, the flag on the CRF** will be used.

* Flag for concomitant medications: *Started prior to first study treatment administration* answered *Yes* on the CRF *Previous/Concomitant Medication* page,

** Flag for medical history: *Ongoing at Informed Consent signature* answered *Yes* on the CRF *Medical History* page.

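### For adverse events dated on the dosing day with no onset time, the SAP excludes only those ending exactly at dosing, so one recorded as ending earlier still counts as treatment-emergent

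*SAP*

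**What the plan says.** The base definition is the same in both documents. Protocol 10.2.4.1 opens with "TEAEs are those AEs with onset date/time" and requires that onset to be no earlier than administration and no more than 48 h after it. SAP 7.2.1.2 repeats this, with the upper limit at "48 h after date/time of study treatment administration". The protocol leaves missing or incomplete AE times to the SAP.

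For a missing onset time, SAP 7.2.1.2 adds two rules:

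- **Inclusion.** An AE whose time "of onset is missing will be counted as treatment-emergent if onset" date lies between the dosing date and the dosing date plus two days.
- **Exclusion.** An AE without an onset time whose "end date and time are identical to study treatment start date and time, is not a treatment emergent AE".

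On data collection, protocol 9.3.1 states: "All AEs with an onset date after a subject has provided informed consent and up to the EOS must be recorded". The same section lists the onset of an AE as a date and a time, but its resolution as a date only.

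**The concern.** When onset time is missing, the end of the event can still settle the order. If an AE was over before the injection, it began before the injection. The exclusion rule uses the end time for this purpose, but tests for equality with the dosing time instead of for being no later than it. An event that stopped at the dosing minute is removed, and one that stopped ten minutes earlier stays in.

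The case is plausible in this trial. AEs are recorded from consent, and protocol Table 2 has a pre-dose AE assessment. Randomization must fall within 6 hours of symptom onset (protocol 4.3), and "Injection of ACT-246475 will be performed as soon as possible after randomization" (protocol 3.1). Neither document says that consent and dosing share a calendar date, but it is a fair inference that they usually will. A date-only rule then cannot separate pre-dose from post-dose events. At stake is whether events that cannot have been caused by the drug may enter the treatment-emergent AE (TEAE) tables, including those for serious AEs (SAEs) and for AEs of special interest (AESIs) such as haemorrhage.

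**Working it through.** The plan gives no figure to reproduce, so the check applies the rule as written to test cases.

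**Inputs.** The inclusion and exclusion rules are from SAP 7.2.1.2. The dosing time of 14:00 is an assumption for illustration. Onset time is missing in every case.

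| Onset date | Recorded end | SAP as written | With 'on or before' |
|---|---|---|---|
| Dosing day | 13:00, 60 min before dosing | TEAE | Not TEAE |
| Dosing day | 13:59, 1 min before dosing | TEAE | Not TEAE |
| Dosing day | 14:00, at dosing | Not TEAE | Not TEAE |
| Dosing day | 14:01, 1 min after dosing | TEAE | TEAE |
| Dosing day | End time missing | TEAE | TEAE |
| Day before dosing | 13:00 on dosing day | Not TEAE | Not TEAE |
| Day before dosing | 14:00 on dosing day | Not TEAE | Not TEAE |

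Only the first two rows change. In both, the recorded end proves that onset preceded the injection, so the base definition is not met. Events with an unresolved order (end after dosing, or end time missing) stay treatment-emergent under either wording.

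**Does another section repair this?**

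- SAP Appendix D says: "An incomplete (missing day or month) or missing AE/concomitant therapy date will be imputed as described in Table 5". Table 5 covers dates that are absent or lack a day or month. It has no rule for a complete date with a missing time.
- The flag in Table 5 for starting before first dose sits in the incomplete-date column, and its footnote defines it on the medication page.
- SAP 10.1 accepts that the treatment period may be over-estimated when times are missing. It does not address an event with a known pre-dose end.

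**Does the SAP's own logic agree with the rule?** It does not.

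- SAP 10.2.2 assigns an event to the post-baseline period only when it cannot be allocated to baseline.
- For incomplete onset dates, Table 5 moves onset to the treatment start date only if resolution is on or after treatment start, or is missing.

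Both default to post-dose only while the timing is unresolved.

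**Size.** One subject in an arm of 21 is 1/21 = 4.8 percentage points; in the overall column of 42 it is 1/42 = 2.4 points. The incidence tables in SAP 7.2.2 count subjects, so this applies only if the subject has no other event in the same row. Otherwise the row does not change.

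**The case against.** The strongest objection is that the problem may rarely or never arise. It needs a missing onset time although protocol 9.3.1 requires one, a recorded end time although that section lists only a resolution date, an onset date equal to the dosing date, and an end before the injection. If end time is not on the form, neither the present exception nor a corrected one can operate. This stands. It limits the size of the point and adds a condition to the remedy.

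A second objection is that over-inclusion is a deliberate and conservative choice when times are missing, as SAP 10.1 acknowledges. That holds for events whose order relative to dosing is unknown. A reader might infer that the whole date-only fallback contradicts the TEAE definition. The documents do not support that: the base definition needs an onset time, and the protocol hands missing times to the SAP. Only the subset with a known pre-dose end conflicts.

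Third, protocol 3.2 makes the safety presentation purely descriptive, and SAP 7.2.2 lists all AEs, so an odd case would be visible. Tables of treatment-related TEAEs rest on the investigator's causality judgement (SAP 7.2.1.3), so an event known to precede the injection is unlikely to enter them. Both remarks are fair. They lower the importance of the point without making the rule correct.

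**Conclusion.** The rule is wrong as written for one narrow class: AEs with no onset time, an onset date equal to the dosing date, and a recorded end earlier than the injection. These are counted as treatment-emergent although they cannot meet the definition.

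The importance is minor. The error can only over-count, it is confined to descriptive safety tables, and it leaves the primary pharmacodynamic analysis alone. The 4.8 points is a ceiling per affected subject on the planned 21 per arm, subject to the row condition above.

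Two stronger readings are tempting. One is that pre-dose events will appear in the TEAE, SAE and haemorrhage tables; the documents show only that the rule would allow it if such events occur. The other is that nearly all same-day pre-dose events would be misclassified because only a single end minute is excluded. That describes the rule's coverage of clock times. It is not a frequency of events, and neither document supplies one.

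The conclusion assumes that AE end time is recorded, at least for some events, as SAP 7.2.1.2 presumes.

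**What to change.** 1. In SAP 7.2.1.2, change the exclusion from an end date and time 'identical to' the study treatment start to one 'on or before' it. The cost is a few words in the SAP and one comparison operator in the program.
2. Reconcile protocol 9.3.1, which lists only a date of resolution, with SAP 7.2.1.2, which relies on an end time, and state whether end time is captured. If it is not, replace the exclusion with an AE indicator for start before study treatment. That costs more: a field on the AE form, or a data query if collection is under way.

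No separate wording is needed for SAEs or AESIs. SAP 7.2.2 summarizes TEAEs for every AE variable in section 7.2.1, so the correction carries through.
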